
Outcome measures section below.

Randomisation

Randomisation of schools to one of the two treatment arms took place on the 29th September 2021. In total, 201 schools were randomised to either the intervention or control group. Randomisation was conducted in Stata by a member of the evaluation team who was not blind to school identities, however, to verify independence, the randomisation code and outcome was checked by an independent staff member who was not part of the evaluation team. The randomisation was stratified by TL region with schools as the unit of randomisation, and (Year 3) pupils as the unit of analysis. A tailored package in Stata (`randtreat`) was used to implement the cluster randomisation with regional stratification. The code used to randomise schools as well as all relevant variables has been saved and can be made available if requested. This code will be included in the final Evaluation Report at the conclusion of the study. The allocation was recorded in Excel and communicated to the implementation team.

As specified in the Evaluation Protocol, randomising at the school level was perceived to reduce the chances of contamination between randomised groups as TAs would be delivering to all identified children in the school. Furthermore, regional stratification was deemed appropriate given the regional nature of delivery, with one TL delivering the training in each region (hence why we refer to 'TL regions'). Regions included in the randomisation as stratifiers were: Cambridgeshire, Derbyshire, Devon, East Sussex, Essex, Greater Manchester, Merseyside,² Nottinghamshire, South Yorkshire, Suffolk, West Sussex, West Yorkshire.

Randomisation occurred with a 50:50 allocation to treatment and control. Schools allocated to treatment receive IWM+A training and are expected to deliver the IWM+A intervention, while schools allocated to control are expected to carry on with business as usual (BAU), and do not receive the training. Schools assigned to the control group will be given £1,000 on completion of all endline assessments. These funds are to be used at the discretion of the school and could be used to buy an intervention programme of their choice, including IWM+A from September 2022. The value of the incentive is the same as was used in the efficacy trial.

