¹¹ There is a convention in some disciplines that a 10pp (or larger) difference in treatment and control means at baseline constitutes 'imbalance' is thus justification for including those measures in sensitivity analyses, but there are counter-arguments to this idea. See Roberts, C. and Torgerson, D. (1999) 'Baseline imbalance in randomised controlled trials', *BMJ*, 319:185; de Boer et al. (2015) 'Testing for baseline differences in randomized controlled trials: an unhealthy research behavior that is hard to eradicate', *International Journal of Behavioral Nutrition and Physical Activity*, 12:4.

The FIML approach will be implemented using the `sem` command in Stata.¹²

Compliance

As the ITT approach captures the averaged effect of *offering* the intervention, we also propose to look at treatment effects in the presence of compliance at the pupil level to capture the average effect of *participation* in IWM+A.

For the purpose of this evaluation, we are employing the EEF's definition of compliance as 'the extent to which the critical ingredients of the intervention are delivered to and/or received by the target participants' (EEF, 2019b). In collaboration with the EEF and the delivery team at University of Oxford, we have defined 'compliance' as pupil attendance at sessions, which will be collected by TAs using attendance logs using a template developed by the delivery team. TAs will be asked to share the logs with the evaluator after all sessions have been completed. As shown in Table 5, children who have attended all five WM sessions and at least four arithmetic sessions will be marked as compliant; all those that do not obtain this will be marked as non-compliant. This is in line with the expectations set-out by the project team.

Table 5. Pupil level compliance measure

Compliance criterion	Data source	Compliance indicator
Attendance at WM sessions	Register of pupil attendance recorded by TAs	Pupil has attended all five WM sessions
Attendance at arithmetic sessions	Register of pupil attendance recorded by TAs	Pupil has attended at least four out of five arithmetic sessions

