There will be two strands to the compliance analysis based on the measure outlined in Table 5. The core component of the compliance analysis will take compliance as a binary measure (where 1=compliant; 0=non-compliant, as defined Table 5), defined at the pupil level, based on attendance as recorded by the TAs. In a situation of imperfect compliance, whereby not all participating pupils are deemed compliant using the criteria outlined in Table 5, we will undertake a complier average causal effect (CACE) analysis, by drawing on an instrumental variable (IV) approach, and using a two-stage least squares (2SLS) estimation approach to recover the treatment effect for those who complied with assignment. The first stage of this approach estimates the extent to which the assignment to IWM+A encourages pupils to take up the treatment (the first stage regresses treatment assignment on compliance). This will estimate a compliance rate. Results for the first stage will report the correlation between the instrument and the endogenous variable; and an F test. The second stage of the IV estimation predicts the outcome as per Equation (1), but substitutes the treatment indicator ($IWMA_{i,t}$ in Equation (1)) with the compliance rate estimated in the first regression (Angrist & Krueger, 1991; Angrist, 2006). The results of this model will answer the research question: To what extent does *compliance with IWM+A* implementation requirements lead to improved outcomes for pupils? This model will be estimated for the primary outcome measure only.

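### The SAP states the CACE first stage in reverse (assignment on compliance), which contradicts the standard IV/2SLS procedure described in the rest of the same paragraph

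*SAP*

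**What the plan says.** The SAP, under Compliance, defines a binary pupil-level indicator: "children who have attended all five WM sessions and at least four arithmetic sessions will be marked as compliant". If compliance is imperfect, it plans a CACE analysis of the primary outcome, "using a two-stage least squares (2SLS) estimation approach to recover the treatment effect for those who complied with assignment".

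It describes the first stage in these terms:

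- Purpose: "The first stage of this approach estimates the extent to which the assignment to IWM+A encourages pupils to take up the treatment".
- Regression, in a parenthesis closing the same sentence: "the first stage regresses treatment assignment on compliance".
- Output: "This will estimate a compliance rate".
- Diagnostics: "Results for the first stage will report the correlation between the instrument and the endogenous variable; and an F test".

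The second stage is Equation (1) with the assignment indicator replaced "with the compliance rate estimated in the first regression". If non-compliance exceeds 10%, a dosage model (0 to 10 sessions attended) is to be fitted by the same approach.

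**The concern.** To regress A on B means that A is the dependent variable. In 2SLS the endogenous variable (compliance) is regressed on the instrument (assignment). Its fitted values then vary only with assignment and the covariates, which is how the estimate keeps the protection of randomisation. The parenthesis has the two variables the other way round.

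The direction matters because the section describes inserting a first-stage fitted value into the second stage. If assignment were the dependent variable, the fitted value would be a linear function of each pupil's own attendance, and the second stage would compare attenders with everyone else. That brings back the selection that an instrumental variable is meant to remove. The section gives no first-stage equation, no first-stage covariates and no IV command, although the SAP names Stata commands for other analyses. Nothing more formal is available to settle the point.

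**Working it through.** The SAP gives no figure for the CACE, so there is none to reproduce. The check has two parts.

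**1. Which direction does each statement imply?** Write Z for assignment, D for compliance and Y for the BAS3 score.

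| Statement in the Compliance section | Direction implied |
|---|---|
| First stage measures how far assignment encourages take-up | D on Z |
| Parenthesis | Z on D |
| First stage yields a compliance rate | D on Z (Z on D would yield predicted assignment) |
| Second stage uses that compliance rate | D on Z |
| Named method is IV/2SLS with an instrument and an endogenous variable | D on Z |

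One statement conflicts with four.

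**2. What would the parenthesis give if carried out literally?**

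Inputs from the SAP:
- 50:50 allocation (Randomisation; 100 and 101 schools).
- No control access, taken from "schools allocated to control are expected to carry on with business as usual (BAU), and do not receive the training". Control schools could buy the programme only from September 2022, after the May 2022 endline.
- An illustrative complier effect δ = 0.24, the efficacy-trial effect size given in the Introduction.

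Assumptions not in the SAP:
- c, compliance in the intervention arm.
- s, the outcome advantage in SD, without the intervention, of pupils who would comply over those who would not.

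Reversed first-stage slope, without covariates:

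b = cov(Z,D)/var(D) = 0.25c / [0.5c(1 − 0.5c)] = 1/(2 − c)

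This is 0.909, 0.769 and 0.667 at c = 0.9, 0.7 and 0.5. The fitted value is a + bD, so the second-stage coefficient is the as-treated contrast divided by b, that is, multiplied by (2 − c).

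As-treated contrast: pupils with D = 1 are all complier types. Among pupils with D = 0, the share of complier types is 0.5c / (0.5 + 0.5(1 − c)) = c/(2 − c). Hence

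as-treated = δ + s[1 − c/(2 − c)] = δ + 2s(1 − c)/(2 − c)

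literal result = (2 − c) × as-treated = δ(2 − c) + 2s(1 − c)

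The correct first stage (D on Z) gives ITT/c = cδ/c = δ = 0.24 in every cell below.

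| c | s = 0 | s = 0.3 | s = 0.5 |
|---|---|---|---|
| 0.9 | 0.24 × 1.1 = 0.264 | 0.264 + 0.06 = 0.324 | 0.264 + 0.10 = 0.364 |
| 0.7 | 0.24 × 1.3 = 0.312 | 0.312 + 0.18 = 0.492 | 0.312 + 0.30 = 0.612 |
| 0.5 | 0.24 × 1.5 = 0.360 | 0.360 + 0.30 = 0.660 | 0.360 + 0.50 = 0.860 |

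The first column is rescaling alone; the others add selection.

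This was checked by simulation: 400 trials per scenario, 201 schools of 10 pupils, ICC 0.16 (the SAP's value), no covariates, c = 0.60, 0.75 and 0.90, and s = 0, 0.3 and 0.5. Correct 2SLS averaged 0.232 to 0.245 across the nine scenarios. The literal version averaged 0.255 to 0.733, within 0.01 of the formula in each. At c = 0.75 and s = 0.3, for example, IV gave 0.239, the as-treated contrast 0.359 and the literal version 0.448; the formula gives 0.24 × 1.25 + 2 × 0.3 × 0.25 = 0.45.

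**The case against.** The strongest reply is that nobody would carry out the parenthesis. The opening of the same sentence, the compliance-rate output, the second-stage substitution and the named estimator all specify the correct direction. A regression with assignment as the outcome cannot produce the compliance rate that the second stage needs, so the parenthesis cannot be followed together with its neighbours. A packaged IV routine, given assignment as instrument and compliance as endogenous variable, would not make the mistake. The analysis is also supplementary to the intention-to-treat result.

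Most of this stands, and it limits the point. A reader might infer that following the SAP yields an as-treated comparison. The section as a whole does not support that: it holds only if the parenthesis is read alone, and even then the result is an as-treated contrast rescaled by (2 − c). A reader might also take this CACE to be the only planned estimate of the effect of participation. It is not, because the dosage model is a second one when non-compliance exceeds 10%.

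What the reply does not remove is that the one phrase stating the regression is wrong. A pre-specified plan should not rely on the analyst to override it.

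**Conclusion.** The parenthesis is reversed and contradicts the paragraph around it. This is a specification error in wording, and the surrounding text shows that a standard IV analysis was intended. It is worth correcting because it is a stated analysis rule for the primary outcome and the dosage model reuses it.

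The size is hypothetical and applies only to a literal reading: a true 0.24 becomes about 0.26, 0.31 or 0.36 at c = 0.9, 0.7 or 0.5 with no selection, and more with positive selection. These figures assume 1:1 allocation, no control access, no covariates and a binary compliance indicator; c and s are not in the SAP. The factor (2 − c) does not carry over to the 0-to-10 dosage variable, which inherits the wording but not this arithmetic. The intention-to-treat analysis of the primary outcome does not depend on the phrase.

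**What to change.** Replace the parenthesis and the second-stage description with wording such as: the first stage regresses pupil compliance on treatment assignment and the Equation (1) covariates (EYFSP score and region strata); the second stage regresses the BAS3 score on predicted compliance and the same covariates; the two stages are estimated jointly as IV, with standard errors that account for clustering by school.

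Reversing the two nouns would cure the contradiction. The further detail is worth adding because the section lists no first-stage covariates and does not say how clustering enters the IV estimate.

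Apply the same wording to the dosage model, with number of sessions attended in place of binary compliance. The cost is a sentence or two of SAP text, with no extra data or resources.

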Appendix A: Pilot testing of BAS3

To understand better the psychometrics of the BAS3 for the eligible population in this trial, TMs administered BAS3 tests to a small sample of pupils (N=72) in Phase 1, with training in the BAS3 number skills subscale being delivered by Oxford University. Researchers from RAND Europe analysed the results from the pilot testing to understand if concerns that arose in the efficacy trial were present. The results of this analysis are presented in Table 6 and Figure 1.

The pilot test was administered to 72 children, and raw scores were available for 69 children,¹⁴ while age standardised score were constructed for 53 pupils.¹⁵ The BAS3 raw scores could range between 0 and 33, while in the sample the raw scores ranged between 4 and 32 based on data for 69 children. The mean raw score was 13.7, with a standard deviation of 5.8. Based on the items administered and the age of the children in the sample we constructed the age-standardised score that could range between 55 and 145. In the sample of 53 pupils for which an age-standardised score could be constructed, scores ranged between 76 and 126. The mean age-standardised score was 98.1, with a standard deviation of 13.6.

[figure not shown]
Table 6. BAS3 descriptive statistics

	Raw score	Age standardised score
N=	69	53
Mean	13.7	98.1
Standard deviation	5.8	13.6

Histograms showing the distribution of BAS3 raw and age-standardised scores are provided in Figure 1. Given the small sample size the histograms do not show perfect normal distribution, but they demonstrate that there is no evidence of ceiling or floor effects in the BAS3.

[figure not shown]
Figure 1. Histogram showing the distribution of BAS3 raw and ability score

Figure 2a Raw score

Note: raw scores can take any value between 0-33. This histogram includes data for n=69/72 pupils.

Figure 2b Age standardised score

Note: age standardised scores can take any value between 55-145. This histogram includes data for n=53/72 pupils.

¹⁴ Raw scores could not be calculated for n=3 pupils as the exact item blocks that they were administered could not be determined.

¹⁵ The lower sample size for the age standardised score was due to missing information about pupil date of birth and/or the exact item blocks that were administered being inconclusive, which meant that the age standardised score could not be calculated even if the raw score was available.
